8. ETHICAL CONSIDERATIONS
9. STATISTICAL ANALYSIS
10. STUDY COSTS
11. PUBLICATION OF RESULTS
12. SPONSOR ROLE AND RESPONSIBILITY
13. REFERENCES

1. INTRODUCTION

Fibromyalgia is a chronic disorder of uncertain aetiology, characterized by widespread pain, muscle tenderness, and decreased pain threshold to pressure and other stimuli.¹ Its pathophysiology is still elusive, although evidence support a derangement in pain processing and modulation.¹ Clinical manifestations of fibromyalgia encompass a large range of symptoms including fatigue, unrefreshing sleep, cognitive and memory disturbances ("*fibro fog*"), anxiety, depression, chronic headache, gastrointestinal problems and more.¹

Obesity is a well-known aggravating factor for musculoskeletal pain, such as in knee osteoarthritis.² Epidemiological data show that fibromyalgia patients have higher prevalence of obesity (40%) and overweight (30%) and that excess of body weight influences course and activity of fibromyalgia.² Similarly, obesity influences pain and progression of knee osteoarthritis.³

In the last years, a new nutritional approach – namely Very Low Calorie Ketogenic Diet (VLCKD) – has been proposed as a potential therapeutic option in different diseases that shares common clinical and pathophysiological features with fibromyalgia and osteoarthritis.⁴

The core characteristics of the VLCKD are the association of a high amount of fat, with low carbohydrate intake, usually a macronutrient ratio of fat to protein and carbohydrate combined equal to 3–4:1.⁴ The objective is to achieve ketosis, leading to reduced insulin secretion and glycaemia within 48h.⁴ Ketosis is achieved when less than 50 g of carbohydrates per day are introduced, with either restricted or unrestricted fat and calorie intake.⁵

VLCKD have been demonstrated to provide clear clinical benefits in different diseases - in particular refractory epilepsy⁶ - and to achieve rapid weight loss in obese subjects who failed other dietetic interventions.⁷ For their efficacy and safety profile, VLCKD entered as a therapeutic options in recent guidelines for management of obesity.^{8,9}

Furthermore, other studies evaluated the effect of VLCKD on conditions that shares common pathophysiological and clinical background with fibromyalgia. Accumulating evidence suggest positive effects on mood¹⁰, cognitive functions,¹¹ as well as an improvement in nociception¹² and sleep quality.¹³

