6. STUDY PROTOCOL

6.1 Study periods

As already mentioned, the study will be conducted following different periods:

1. **Free diet (4 weeks, Phase 0).** After recruitment (T-4), the patient will enter "free diet phase" in which he/she will be asked to follow a normal free diet for 4 weeks. During this period, a nutritional interview will be carried out by a trained dietician who will elaborate a personalized diet and order the ketogenic products on the basis of patient's preferences.
2. **VLCKD (8 weeks, Phases 1-3).** After the free diet period, the patient will start the VLCKD regimen as described (4.1 and "VLCKD" attachment). At the beginning of this period (T0) a box with the commercial products necessary to cover the whole study period will be hand-delivered by a dietician that will instruct the patient on the correct use and storage.
3. **Maintenance (12 weeks, Phases 4-6).** After VLCKD phase, the patient will start maintenance period as described (4.1 and "VLCKD" attachment).

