6.2 Timing of disease activity and weight assessment

Study procedures are graphically summarized in the attachment "Study chart".

Patient-reported outcomes described in 5.1 and 5.2 will be obtained at T-4, T0, T1, T2, T3, T4, T5, T6, T7, T8, T12, T16, and T20. Patients will be instructed to fill the questionnaires at appropriate intervals and bring them at the subsequent office visits.

During the office visits (T0, T8, T12, T16, T20), a rheumatologist will perform medical interview with special focus on adverse events and routine musculoskeletal visit; weight and height will be measured and recorded.

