9. STATISTICAL ANALYSIS

Given the exploratory nature of the study, an arbitrary number of 20 fibromyalgia and 20 symptomatic knee osteoarthritis patients will be recruited from Rheumatology Outpatient Clinic – IRCCS Istituto Ortopedico Rizzoli, Bologna, Italy. Patients' associations will be involved for volunteer engagement.

Primary measures of efficacy (change in FIQ total score and WOMAC total score, for fibromyalgia and osteoarthritis, respectively) will be compared using paired-sample Student's T tests at time T-4, T0, T8, T20. Analysis of covariance (ANCOVA) will be used to evaluate the effect of baseline disease severity and BMI on change in primary efficacy measures.

Furthermore, other exploratory analyses will be performed:

- Change in secondary outcome measures at T-4, T0, T8, T20;
- Correlation between change in body weight ($\Delta\text{weight}_{T0-T8}$) and change in primary (ΔFIQ_{T0-T8} or $\Delta\text{WOMAC}_{T0-T8}$) and secondary outcome measures;
- Time course of %change in FIQ total score and WOMAC total score from T-4 to T20;
- Student's T test for difference in ΔFIQ_{T0-T8} or $\Delta\text{WOMAC}_{T0-T8}$ in patients who achieved and maintained ketosis during the ketogenic phase (urinary ketones > +5 from week 1 to week 8) vs patient who did not maintained ketosis.

Both per-protocol (PP) and intention-to-treat (ITT) analyses will be performed.

All analyses will be performed using the Statistical Software for Social Sciences (SPSS, IBM) version 23.

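### The ANCOVA of change on baseline severity has no comparison group; if severity is the score the change starts from, its slope is biased by regression to the mean

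*Protocol*

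**What the plan says.** Section 9 names the "change in FIQ total score and WOMAC total score, for fibromyalgia and osteoarthritis, respectively" as the primary measures. They "will be compared using paired-sample Student's T tests at time T-4, T0, T8, T20". The next sentence adds the analysis at issue: "Analysis of covariance (ANCOVA) will be used to evaluate the effect of baseline disease severity and BMI on change in primary efficacy measures".

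The protocol does not say which instrument measures severity, whether baseline is T-4 or T0, or over which interval the change is taken. Three other parts bear on the reading:

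- Sections 5.1 and 5.2 list the disease-activity tools. FIQ and WOMAC come first and are the only disease-specific scales; the rest are SF-36, EQ-5D and, for fibromyalgia, HADS.
- The other change scores in Section 9 that carry an interval label run from T0 to T8.
- Sections 2.1, 4.1 and 6.1 describe no control arm. Each patient is "asked to follow a normal free diet for 4 weeks" and then starts the VLCKD. Section 6.2 has "Patient-reported outcomes described in 5.1 and 5.2 will be obtained at T-4, T0" and later visits, so two pre-diet scores exist for every patient.

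**The concern.** In a controlled trial, a baseline covariate sharpens a comparison between groups, and regression to the mean affects the groups alike. Here there is no group term. What the ANCOVA delivers is the coefficient of severity (and of BMI) on change, described as an effect.

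If severity is the score at the start of the change, a patient who happens to score high that day has both a high severity value and, on average, a larger later fall. Patients who look more severe then seem to improve more, even if the diet helps everyone equally.

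At stake is a secondary message. A pilot that reports better response in more severe patients may shape who is enrolled or stratified in the next trial, when the slope may reflect nothing but fluctuation between visits.

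**Working it through.** The protocol states no alpha, SD, reliability or test-retest correlation and calls its sample size arbitrary, so there is no figure of its own to reproduce.

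**Inputs from the protocol.** 20 patients per disease and two covariates, severity and BMI (Section 9), which leaves 20 - 3 = 17 residual df; scores at T-4, T0 and T8 (Section 6.2).

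**Assumed inputs.** Two-sided 5% test; score variance 1 at T-4 and T0; reliability ρ from 0.5 to 0.9; response R independent of true severity, with SD s from 0 (equal response) to 1.0 baseline SD.

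**Step 1: slope on the starting score.** Write Y0 = T + e0 and Y8 = T + R + e8, with Var(T) = ρ and independent errors of variance 1 - ρ. Then Cov(Y8 - Y0, Y0) = -Var(e0) = -(1 - ρ), and Var(Y0) = 1. The slope is -(1 - ρ): -0.50 at ρ = 0.5, -0.30 at 0.7, -0.20 at 0.8, -0.10 at 0.9. The correct value for no severity effect is 0.

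**Step 2: how often it is significant.** The correlation of change with the T0 score is -(1 - ρ)/√(2(1 - ρ) + s²). At ρ = 0.8 it is -0.2/√0.40 = -0.32 for s = 0, and -0.2/√0.65 = -0.25 for s = 0.5. Simulation (40,000 trials per scenario, n = 20, severity and BMI in the model) gives these rejection rates with no true severity effect:

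| Response SD | ρ = 0.5 | 0.6 | 0.7 | 0.8 | 0.9 |
|---|---|---|---|---|---|
| 0 | 62% | 50% | 39% | 27% | 15% |
| 0.5 | 50% | 39% | 28% | 18% | 10% |
| 0.75 | 42% | 30% | 21% | 13% | 7% |
| 1.0 | 33% | 24% | 17% | 11% | 6% |

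**Step 3: T-4 score as covariate, T0-T8 change as outcome.** The slope becomes Cov(Y8, Y-4) - Cov(Y0, Y-4). With independent visit errors this is ρ - ρ = 0, and the simulated rejection rate is about 5%.

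If scores are serially correlated, with correlation r per 4 weeks, the slope on T0 is r² - 1, the slope on T-4 is r³ - r, and the run-in slope (T-4 to T0 change on the T-4 score) is r - 1. With equal response:

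| r | T0 slope, rejection | T-4 slope, rejection | Run-in slope |
|---|---|---|---|
| 0.7 | -0.51, 62% | -0.36, 32% | -0.30 |
| 0.8 | -0.36, 46% | -0.29, 30% | -0.20 |
| 0.9 | -0.19, 25% | -0.17, 21% | -0.10 |

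Two intermediate cases:

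- Correlations of 0.85 (T-4 with T0), 0.75 (T0 with T8) and 0.68 (T-4 with T8), equal response: the T0 slope is 0.75 - 1 = -0.25 with 32% rejection; the T-4 slope is 0.68 - 0.85 = -0.17 with 17%.
- A stable component plus a decaying one plus noise, response SD 0 or 0.5: 20-53% with T0, 6-8% with T-4.

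The T-4 rate was below the T0 rate in every case run.

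**Step 4: power of the T-4 model.** At ρ = 0.7-0.8 and response SD 0 or 0.5, power is 15-32% for a true slope of -0.3 and 31-64% for -0.5.

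**The case against.** The strongest reply is that the protocol does not commit to the faulty version. Instrument, visit and interval are details that a statistical analysis plan usually settles, and that plan is not at hand. T-4 is a live candidate for baseline: patients are recruited then (Section 6.1), and the time course in Section 9 starts there. T-4 severity with T0-T8 change is therefore already allowed. SF-36, EQ-5D and HADS could also serve as severity measures.

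Further, the slope is a valid description of change by observed starting score, the protocol nowhere claims that severe patients respond better, and the study calls itself exploratory. The rejection rates span a tenfold range because reliability is assumed, and the T-4 covariate does not fully cure the problem.

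Much of this stands: the covariate is not fixed by the text, the size is assumption-driven and the remedy is partial. What does not stand is that only a detail is missing. Section 9 commits to evaluating an effect of severity on change where no group contrast exists, and its most natural implementation gives a biased slope for that effect. Taking T-4 as baseline is no escape if the change is also counted from T-4. The direction of the bias does not depend on the assumed reliability, provided it is below 1 and the score SDs are similar across visits.

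**Conclusion.** The point holds in conditional form and is minor. If severity is the FIQ or WOMAC total from which the change is computed, the slope is biased by -(1 - reliability) toward larger apparent improvement in more severe patients. For assumed reliability 0.8-0.9 and response SD 0.5-1.0, a nominal 5% test at n = 20 rejects in about 6-18% of trials. The 62% figure needs reliability 0.5 and the same response in every patient.

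Three stronger readings are not supported:

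- *The protocol fixes the starting score as the covariate.* It names neither instrument nor visit.
- *The primary result is affected.* The paired t tests compare mean scores and do not use this slope.
- *The BMI coefficient is also materially biased.* A reader might infer this from the Introduction, which says that "excess of body weight influences course and activity of fibromyalgia" and that "obesity influences pain and progression of knee osteoarthritis". Those statements concern excess weight in general, whereas Section 3.2 admits only BMI of 30 or more, and no correlation within that range is given. In simulation with the T0 score in the model, a null BMI effect was rejected in 5-8% of trials when BMI correlated 0.2-0.3 with true severity. The 15% extreme needed a correlation of 0.5, for which the protocol offers no basis.

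**What to change.** Change Section 9 along these lines:

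> Baseline severity in the ANCOVA is the FIQ (fibromyalgia) or WOMAC (knee osteoarthritis) total at T-4, and the outcome is the T0-T8 change in the same total. Any slope of change on the score from which that change starts is descriptive and will not be taken as evidence that severity modifies response.

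Optionally, show the slope of the T-4 to T0 change on the T-4 score beside it, as a rough picture of regression to the mean before the diet starts. This is a benchmark and not a test: the run-in lasts 4 weeks against 8, and the run-in slope matches the artefact only if visit errors are independent. At r = 0.8 per 4 weeks it is -0.20 against -0.36.

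The cost is a few sentences and no new data. The downside should be stated openly: the T-4 covariate removes the bias only with independent visit errors, reduces it only partly under serial correlation, and has modest power with 20 patients. The descriptive caveat holds under any error structure and should be kept even if the covariate is not changed.

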1.1 Aim of the study

On the basis of this background, aim of this pilot study is to investigate the effects of VLCKD in obese patients with fibromyalgia and symptomatic knee osteoarthritis.

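### Minor: name Welch's test, not Student's, for the exploratory ketosis comparison, because its group sizes are uncontrolled and Student's error rate drifts from 5% if the variances also differ

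*Protocol*

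**What the plan says.** Protocol section 9 sets the sample size as "an arbitrary number of 20 fibromyalgia and 20 symptomatic knee osteoarthritis patients will be recruited". After the primary paired comparisons and the ANCOVA it continues, "Furthermore, other exploratory analyses will be performed", and lists four items. The last is a "Student's T test for difference in" the T0 to T8 change in FIQ (fibromyalgia) or WOMAC (osteoarthritis) "in patients who achieved and maintained ketosis during the ketogenic phase (urinary ketones > +5 from week 1 to week 8"), set against patients who did not maintain ketosis.

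The protocol gives no significance level, no expected ketosis rate and no SDs of change. It mentions neither Welch's test nor the equal-variance assumption. Its software sentence, "All analyses will be performed using the Statistical Software for Social Sciences (SPSS, IBM) version 23", does not settle the variance form either. Section 1.1 calls the trial a pilot.

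**The concern.** In ordinary usage Student's two-sample test pools the two variances. Pooling is safe if the groups have the same variance, and nearly safe if they have the same size. Here neither is under the investigators' control.

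- **Size.** Membership depends on urinary ketones over weeks 1 to 8, so the split is known only afterwards.
- **Variance.** Maintaining ketosis means meeting the threshold throughout weeks 1 to 8. Everyone else falls into the other group, from a patient with one missed week to one who gave up the diet early. Change scores in such a mixture may well vary more. This is reasoning, not something the protocol documents.

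If both differ, the p-value and confidence interval are off, and the direction depends on which group is smaller. A small, more variable group gives intervals that are too narrow and too many false positives. A small, less variable group gives the reverse. Because the ketosis rate is not stated, the direction cannot be foreseen. This is the only listed test that links ketosis itself to symptom change, so its interval should be reliable.

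**Working it through.** The protocol has no figure of its own to reproduce here.

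**Inputs.** From section 9: Student's test, and 20 patients per disease, hence N = 20 at most per comparison. Assumed, because not given: two-sided 5%, normally distributed changes, splits from 10/10 to 17/3, and an SD ratio (smaller group ÷ larger group) from 0.5 to 2.

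**Why pooling fails.** For group sizes n₁, n₂ and SDs s₁, s₂:

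- True variance of the mean difference: s₁²/n₁ + s₂²/n₂.
- Variance that Student's test estimates, on average: [(n₁−1)s₁² + (n₂−1)s₂²]/(n₁+n₂−2) × (1/n₁ + 1/n₂).

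Take s₁ = 1 in the larger group.

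- *Equal SDs, any split:* both equal 1/n₁ + 1/n₂. No distortion.
- *10/10, s₂ = 2:* true 0.1 + 0.4 = 0.5; pooled (9 + 36)/18 × 0.2 = 0.5. The standard error is right on average.
- *12/8, s₂ = 2:* true 1/12 + 4/8 = 0.583; pooled (11 + 28)/18 × 0.2083 = 0.451. The standard error is √(0.451/0.583) = 0.88 of its true value.
- *16/4, s₂ = 2:* true 1/16 + 4/4 = 1.0625; pooled (15 + 12)/18 × 0.3125 = 0.469. The standard error is √(0.469/1.0625) = 0.66 of its true value.
- *16/4, s₂ = 0.5:* true 1/16 + 0.25/4 = 0.125; pooled (15 + 0.75)/18 × 0.3125 = 0.273. The standard error is √(0.273/0.125) = 1.48 times its true value.

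**Actual type I error**, simulated under no difference (200,000 replicates per cell), shown as Student / Welch:

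| Split | SD ratio 0.5 | SD ratio 1 | SD ratio 2 |
|---|---|---|---|
| 10/10 | 5.4% / 4.9% | 5.0% / 4.8% | 5.5% / 5.0% |
| 12/8 | 3.1% / 4.9% | 5.0% / 5.0% | 8.8% / 5.2% |
| 14/6 | 1.5% / 4.8% | 5.0% / 5.2% | 13.1% / 5.4% |
| 15/5 | 1.0% / 4.8% | 5.0% / 5.4% | 15.9% / 5.6% |
| 16/4 | 0.7% / 5.1% | 5.0% / 5.9% | 18.8% / 6.1% |
| 17/3 | 0.4% / 5.9% | 5.0% / 7.3% | 22.1% / 7.2% |

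At an SD ratio of 1.5, Student's error runs from 7.2% (12/8) to 13.7% (17/3). Choosing between the two tests by Levene's test removes only part of the problem: at ratio 2 the error is still 9.6% at 14/6 and 13.8% at 16/4.

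**Price of Welch when the SDs are in fact equal**, for a true difference of 1.5 SD (simulated, 400,000 replicates):

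| Split | Power, Student | Power, Welch | Loss (points) |
|---|---|---|---|
| 12/8 | 87.5% | 86.3% | about 1 |
| 14/6 | 82.7% | 78.0% | about 5 |
| 15/5 | 78.5% | 69.7% | about 9 |
| 16/4 | 71.9% | 57.2% | about 15 |

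At 16/4 the mean 95% CI half-width grows from 1.16 to 1.40 SD.

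**The case against.** The case for leaving the bullet alone has four parts.

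- **The harm needs two things that the protocol does not give:** a marked imbalance and a marked difference in SD. This stands. A reader might infer that self-formed, unequal groups are enough to invalidate Student's test, or that the error in this trial will be far from 5%. Neither follows. Imbalance alone leaves the error at 5.0%, unequal SDs at 10/10 move it to 5.5% at most, and the 19% figure is an extreme corner of an assumed range.
- **The variance form could be settled in a statistical analysis plan, and the equal-variance reading is inferred from the test's name.** The inference is fair to flag, and such a plan may exist. But the protocol is not silent: it names a test whose usual meaning is the pooled form.
- **Nothing confirmatory rests on this p-value.** This stands. The comparison is the last exploratory item, with an arbitrary sample size, and section 1.1 states that the "aim of this pilot study is to investigate the effects of VLCKD in obese patients". That limits the weight of the point but does not make the pooled interval the better one to report.
- **Welch is not free.** This also stands. A reader might take the switch as costless, but at 16/4 with equal SDs the power loss is substantial. The choice trades precision for protection against an unknown variance ratio. Where the loss is small (12/8), the protection gained is also smallest.

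**Conclusion.** The point holds as a minor improvement, conditional on unequal variances. Assuming two-sided 5%, normal changes, N = 20 and SD ratios of 0.5 to 2, Student's actual error ranges from about 3% to 9% at 12/8 and from about 0.7% to 19% at 16/4. Welch's test holds it between about 5% and 6% at those splits. With equal SDs Student's test is correct at every split, and the protocol contains nothing that shows the SDs will differ.

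Two wider conclusions would go too far. The primary paired comparisons are untouched, because this test is separate from them. And a better-calibrated p-value would not make the contrast causal: patients who keep to the diet may differ from the others in ways that affect symptoms, and neither test addresses that confounding.

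**What to change.** In the last exploratory bullet of Protocol section 9, and only there, replace Student's test with Welch's unequal-variance t-test, for FIQ and for WOMAC alike. No other analysis in the section is a two-group t-test. Report the size of each ketosis group and the mean difference with its Welch 95% CI. Do not let a preliminary Levene's test choose the method.

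Add that with three or fewer patients in either group the result is descriptive only, because Welch's test is then itself slightly liberal (about 7% at 17/3 with equal SDs).

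The cost is a sentence or two of text and no new data. The statistical price is the power loss and wider interval shown above for lopsided groups with equal SDs, which an exploratory comparison can bear.

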4. DIETETIC INTERVENTION

4.1 Very low-calorie ketogenic diet (VLCKD)

A personalized VLCKD will be prepared for each patient by specialized dietitians at IRCCS Istituto Ortopedico Rizzoli, Bologna using a combination of commercially-available ketogenic preparations and patient's handmade prepared meals (see attachment "VLCKD"). The commercial preparations will be ordered for free by an authorized supplier (see 9) on the basis of individual choices and preferences expressed during nutritional interview, and delivered by the seller to the Dietetic Service – IRCCS Istituto Ortopedico Rizzoli, and subsequently hand-delivered to patients by a dietician investigator.

Briefly, VLCKD is a nutritional intervention that mimics fasting through a marked restriction of daily carbohydrate intake, usually lower than 30 g/day (\approx 13% of total energy intake), with a relative increase in the proportions of fat (\approx 44%) and protein (\approx 43%) and a total daily energy intake < 800 kcal, depending on the amount and quality of protein preparations. Nonetheless, VLCKD should not be considered as a high-protein diet, since its daily protein intake is approximately 1.2–1.5 g/kg of ideal body weight (BMI 22.5 kg/m²).

According to clinical practice guidelines^{8,9}, VLCKD is based on protein preparations of high biological value derived from green peas, eggs, soy and whey. Each protein preparation is composed by approximately 18 g protein, 4 g carbohydrate, 3 g fat (mainly high-oleic vegetable oils) and provides approximately 100–150 kcal. Therefore, VLCKD is characterized by a low lipid content, mainly deriving from olive oil (\approx 20 g per day).

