4.2 Weight loss program

The weight-loss program will be preceded by a free-diet phase (Phase 0, duration: 4 weeks), during which the patient will be invited to eat normal meals.

The ketogenic period will be divided in three different phases.

During the first phase (Phase 1, duration: 4 weeks), patients are allowed to eat four to six (depending on ideal body weight) of such protein preparations and low-carbohydrate vegetables. Patients will be instructed to maintain the intake of clear liquids (water, tea, coffee or unsweetened carbonated drinks) > 2 L/day.

In the next phases, the state of ketosis is still maintained, but one (Phase 2, duration: 2 weeks) or two (Phase 3, duration: 2 weeks) of the provided meals (lunch or/and dinner) are gradually replaced by natural protein meals (meat/fish/eggs/legumes).

Following the ketogenic period, carbohydrates are gradually reintroduced, starting from foods with the lowest glycaemic load (fruit, dairy products—Phase 4, duration: 4 weeks), followed by foods with moderate (legumes—Phase 5, duration: 4 weeks) and high glycaemic load (bread, pasta and cereals—Phase 6, duration 4 weeks). The gradual reintroduction of food items allows for a progressive nutritional education that supports long-term weight-loss maintenance.

Nutritional details of each phase are reported in the attachment “VLCKD”.

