6.3 Ketosis assessment

Ketosis assessment will be performed using urine strips (Siemens Multistix 10 sg) provided at time of enrolment (T0) at weekly interval from week T0 to T12. Patients will be instructed on correct usage of the strips and to take a picture of urine stick that will be sent by email to a dedicate address for evaluation.

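### The one stated comparison of FIQ or WOMAC change by ketosis status is unadjusted, so a difference could not be read as specific to ketosis

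*Protocol*

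**What the plan says.** Section 9 lists, among its exploratory analyses, a "Student's T test for difference in" the T0-T8 change in FIQ or WOMAC. One group is "patients who achieved and maintained ketosis during the ketogenic phase (urinary ketones > +5 from week 1 to week 8"); the other is everyone who did not maintain ketosis. No covariate is named.

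Two other items in Section 9 come close but do not meet this comparison:

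- "Analysis of covariance (ANCOVA) will be used to evaluate the effect of baseline disease severity and BMI on change in primary efficacy measures". This has no ketosis term and no weight-change term.
- "Correlation between change in body weight" from T0 to T8 and the change in outcome. This is a separate two-variable analysis without ketosis.

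The data for a joint model are already scheduled. Section 6.3 has urine strips read "at weekly interval from week T0 to T12". Section 6.2 has office visits that include T0 and T8, at which "weight and height will be measured and recorded", and questionnaires at both times. Section 4.1 describes the diet as having "a total daily energy intake < 800 kcal".

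**The concern.** Patients place themselves in the two ketosis groups after baseline, largely by how closely they follow the diet. On a diet of this energy content, those who stay in ketosis can be expected to lose more weight as well. The protocol's Introduction names obesity as an aggravating factor for musculoskeletal pain, so weight loss is itself a plausible route to better FIQ or WOMAC scores. The groups may also differ in T0 severity.

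If the maintained group improves more, the planned result could reflect ketosis, weight loss or a different starting point, and it cannot show which. Setting it beside the separate weight correlation does not help, because neither analysis conditions on the other. What is at stake is the interpretation of this one exploratory result.

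**Working it through.** **The plan's own figures.** There is nothing to reproduce. The 20 + 20 patients are declared arbitrary, and the protocol gives no SD, correlation, ketosis rate or effect size. Everything below except n = 20 per disease is assumed and serves only to show scale.

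**Assumptions.** Scores are in within-group SD units; r, the T0-T8 correlation, is 0.3, 0.5 or 0.7; 9 patients maintain ketosis and 11 do not; two-sided 5% level; no dropout.

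**Step 1: weight loss.** Suppose the maintained group loses 1 SD more weight, weight loss correlates ρ = 0.3 or 0.5 with the T0-adjusted outcome, and ketosis has no direct effect. The expected group difference is ρ × √(1 − r²) × 1 SD.

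- Smallest (ρ = 0.3, r = 0.7): 0.3 × 0.714 = 0.21 SD
- Largest (ρ = 0.5, r = 0.3): 0.5 × 0.954 = 0.48 SD

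Simulation gives 0.22 to 0.48 SD.

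| Model | Mean difference | Rejection rate |
|---|---|---|
| Planned t-test | 0.22 to 0.48 SD | 8 to 16% |
| T0 score added | about the same | 9 to 18% |
| T0 score and weight change added | 0 | about 5% |

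T0 score alone does nothing about weight loss; the weight term is what matters here. If weight loss lies on the path from ketosis to symptoms, the same 0.22 to 0.48 SD is part of the total ketosis effect and not a bias. The results with and without weight are therefore both needed.

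**Step 2: precision from T0 adjustment.** No T0 gap, true difference 1 SD. The residual SD is √(2(1 − r)) for the change score and √(1 − r²) for ANCOVA. The standard error multiplies this by √(1/9 + 1/11) = 0.449. At r = 0.3 the t-test half-width is about 2.101 × 1.183 × 0.449 = 1.12 SD, and the ANCOVA half-width about 2.110 × 0.954 × 0.449 = 0.90 SD before allowing for chance T0 imbalance. Simulated mean half-widths and power:

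| r | Half-width, t-test | Half-width, ANCOVA | Power, t-test | Power, ANCOVA |
|---|---|---|---|---|
| 0.3 | 1.10 | 0.92 | 0.43 | 0.57 |
| 0.5 | 0.93 | 0.83 | 0.57 | 0.66 |
| 0.7 | 0.72 | 0.69 | 0.78 | 0.81 |

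**Step 3: what T0 adjustment does not do.** Give the groups a T0 gap of 0.5 SD and no effect. The bias is (1 − r) × 0.5 = 0.35, 0.25 and 0.15 SD at the three values of r. It falls on the t-test if the gap would regress, and on ANCOVA, in the opposite direction, if the gap would persist. Each method is unbiased in the case where the other fails. T0 adjustment is therefore justified by precision, not as a cure for confounding.

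**The case against.** **The protocol never promises to isolate ketosis.** Its aim is the effects of the diet, in a pilot, and this comparison is labelled exploratory. Extra covariate models could sit in an SAP that is not shown. This limits the importance of the point but does not remove it: Section 9 itself fixes the test and the contrast, and in that form a positive result invites a reading that it cannot support.

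**The shift is modest.** At matching r, the 0.21 to 0.48 SD is 26 to 50% of the t-test's own half-width (0.29/1.10 to 0.36/0.72). This stands. So does the fragility of the group sizes: if weeks were independent, a weekly ketosis probability of 0.80 would leave about 20 × 0.80⁸ = 3.4 patients in the maintained group, and 0.98 about 17. The fix does not cure this.

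**Stronger readings that a reader might infer, and that the documents do not support:**

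- *The all-eight-weeks split is wrong and should give way to a graded exposure.* The split fits Section 4.2, where in the later ketogenic phases "the state of ketosis is still maintained". Under assumed scenarios, power for split against share of positive weeks is 0.19 against 0.40 if benefit grows with weeks, but 0.65 against 0.32 if only sustained ketosis helps. Neither dominates. Emailed strip pictures may also be missing selectively, which would distort a proportion of available readings.
- *The weekly readings serve no other purpose.* Section 6.3 has the pictures sent in for evaluation, and the per-protocol set is not defined, so a use there cannot be excluded. Only the absence of another stated analysis is supported.
- *Adjusting for T0 makes the groups comparable.* Step 3 of the working shows that it need not.

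**Conclusion.** The point holds in a limited form. The stated ketosis comparison is unadjusted and non-randomised, and no stated model combines ketosis with T0 score or weight change, so a difference could not be read as specific to ketosis. This rests on the text of Section 9 and needs no assumed figure.

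The size does rest on assumptions. With a 1 SD weight-loss gap and correlations of 0.3 to 0.5, weight loss alone would produce roughly 0.2 to 0.5 SD and raise the rejection rate from 5% to 8 to 16%. Smaller gaps or weaker correlations would shrink this. The change is optional and its importance is low: the item is exploratory, and the primary paired tests of FIQ and WOMAC are not touched.

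**What to change.** Keep the planned t-test. Beside it, for each disease and in the same PP and ITT sets that Section 9 already requires, report:

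- (a) the same group comparison by ANCOVA with T0 score as covariate, stated to be for precision and not as proof that confounding is removed;
- (b) model (a) with T0-T8 weight change added, labelled as association beyond weight loss, because weight loss may lie on the causal path.

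Give estimates with 95% confidence intervals, described as exploratory associations only.

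**Cost.** A few sentences in Section 9 and no new data. It adds 2 models × 2 diseases × 2 sets = 8 exploratory estimates. With 20 patients, residual degrees of freedom fall from 18 to 17 in (a) and 16 in (b), and to fewer after dropout. Model (b) removes any association that runs through weight loss and is imprecise: under the working's assumptions with a 1 SD weight gap, its power for a direct effect of 1 SD is 0.49 to 0.80. A null result from (b) should not be read as absence of a ketosis effect.
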